Subjects will be ineligible to participate in this trial if they have received the licensed 2017-2018 licensed seasonal IIV (IIV3 or IIV4, including high dose vaccine for the elderly) any time prior to enrollment; IIV4 will be provided at the first study vaccination to all participants in the study.

Table 1: Study Design

	Day 1 Dose 1	Approximately Day 22 Dose 2	Approximately Day 43 Dose 3
Group 1 (Age 19-64) n=60	Dose 1 (First and Second Study Vaccinations): Sanofi Pasteur H7N9 vaccine 3.75 mcg/ PBS diluent, plus GSK AS03 adjuvant + IIV4	Dose 2 (Third Study Vaccination): Sanofi Pasteur H7N9 vaccine 3.75 mcg/ PBS diluent, plus GSK AS03 adjuvant	N/A
Group 2 (Age 19-64) n=60	Dose 1 (First Study Vaccination): IIV4	Dose 2 (Second Study Vaccination): Sanofi Pasteur H7N9 vaccine 3.75 mcg/ PBS diluent, plus GSK AS03 adjuvant	Dose 3 (Third Study Vaccination): Sanofi Pasteur H7N9 vaccine 3.75 mcg/ PBS diluent, plus GSK AS03 adjuvant
Group 3 (Age 19-64) n=30	Dose 1 (First Study Vaccination): IIV4	N/A	N/A
Total Enrollment, n = ~150	
Blood for HAI/Neut assays for 2017 H7N9 IIV will be collected:
 
 for Group 1 on Days 1 (baseline), 22, and 43, and at approximately 180 days post second adjuvanted 2017 H7N9 IIV dose (Day 202) for Group 2, on Days 22 (baseline), 43, and 64, and at approximately 180 days post second 2017 H7N9 IIV dose (Day 223). 
Serological antibody assays will also be performed against the vaccine viruses in IIV4 from serum samples collected at baseline (Day 1) and approximately 21 and 180 days following receipt of IIV4 (Groups 1, 2 and 3).
 
Safety Lab Timepoints:
 
Group 1: 4 timepoints per subject (Days 1, 8, 22, and 29) Group 2: 6 timepoints per subject (Days 1, 8, 22, 29, 43, and 50) Group 3: 2 timepoints per subject (Days 1 and 8) and Early Termination and /or Unscheduled Visits
		

Figure 1: Schematic of Study Design

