monovalent A/H7N9 vaccine to be used in this study has not been tested for safety in animals and has not previously been evaluated in humans. The DMID, NIAID sponsored two Phase II clinical trials that included an assessment of the safety, reactogenicity, and immunogenicity of two IM doses of a monovalent A/H7N9 vaccine produced by Sanofi Pasteur, Swiftwater, PA, administered with or without AS03 in healthy adults (DMID Protocol 13-0032; NCT01938742 and DMID Protocol 13-0033; NCT01942265).

Overall, the study products administered in both of these clinical trials were generally safe and well-tolerated. For DMID Protocol 13-0032, nine SAEs were reported. All were assessed as being not related to study product. Two cases of Autoimmune thyroiditis (Hashimoto's disease/Hashimoto's thyroiditis) or Adverse Events of Special Interest (AESIs) were reported in this clinical trial: one case was assessed as not related to study product (due to preexisting Thyroid Peroxidase Antibodies) and the second case was assessed as related to study product (no preexisting Thyroid Peroxidase Antibodies).

For DMID Protocol 13-0033, sixteen SAEs were reported, fifteen of these SAEs were assessed as being not related to study product. One SAE was considered to be related: acute inferior myocardial infarction. Two AESIs were reported in this clinical trial: psoriasisiform dermatitis and celiac disease (both assessed as not related to study product because both disorders pre-existed to vaccination, but both disorders received the diagnosis after vaccination).

The current monovalent split IIV was derived from the influenza virus A/Hong Kong/125/2017 (H7N9). The manufacturing process for the production of this investigational A/H7N9 vaccine is similar to the process used to produce the licensed Influenza Virus Vaccine Fluzone® family of products. As such, the safety profile of the candidate A/H7N9 vaccine should be similar to the current Fluzone® vaccine.

[REDACTED] formulation has been determined by [REDACTED]

[REDACTED] In this clinical trial, the labeling of the original [REDACTED] The vaccine preparation has been adjusted to meet the targeted concentration by [REDACTED]

[REDACTED] was produced in accordance with the commercial process [REDACTED]

[REDACTED] The final vaccine preparation is [REDACTED]

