9.5 Halting Rules

For the purpose of halting rules only events that occur following the administration of the **AS03 adjuvanted 2017 H7N9** will be considered. Further enrollment and study vaccinations will be halted for DSMB review/recommendation if any of the following are reported:

- Any subject experiences ulceration, abscess, or necrosis at the injection site related to study product administration.
- Any 2 or more subjects experience laryngospasm, bronchospasm, or anaphylaxis within 1 day after administration of study product that is considered related to study product.
- Three or more subjects experience generalized urticaria (defined as occurring at more than two body parts) within 3 days after administration of study product that is considered related to study product.
- Any subject experiences an SAE from the time of the first 2017 H7N9 vaccination through 14 days after each 2017 H7N9 vaccination.
- Any subject experiences acute weakness of limbs and/or cranial nerve innervated muscles (description of potential signal of GBS) after administration of study product.
- Any subject develops a PIMMC after administration of study product through the subject's last study visit.

This trial will also be halted for DSMB review/recommendation if, within 7 days after administration of any study vaccination, any of the following occurs within the 2017 A/H7N9 IIV AS03-adjuvanted treatment arms (Group 1 or Group 2).

- 7% or more of subjects (with a minimum of 3 subjects) who received at least one dose of study vaccine to date, cumulative to all 2017 H7N9 vaccine administrations, across Groups 1 and 2, experience the same severe (Grade 3) study vaccine-related injection site reaction. Ecchymosis, erythema, and induration (hardness)/edema (swelling) will also be measured in mm but size will not be used as halting criteria.

- 7% or more of subjects (with a minimum of 3 subjects) who received at least one dose of study vaccine to date, cumulative to all 2017 H7N9 vaccine administration, across Groups 1 and 2, experience the same severe (Grade 3) study vaccine-related subjective systemic reaction, for which the severity (grade) is corroborated by study personnel.
- 7% or more of subjects (with a minimum of 3 subjects) who received at least one dose of study vaccine to date, cumulative to all 2017 H7N9 vaccine administration, across Groups 1 and 2, experience the same severe (Grade 3) study vaccine-related quantitative systemic reaction.

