- 7% or more of subjects (with a minimum of 3 subjects) who received at least one dose of study vaccine to date, cumulative to all 2017 H7N9 vaccine administration, across Groups 1 and 2, experience the same severe (Grade 3) study vaccine-related clinical safety laboratory AE.

Grading scales for solicited injection site and systemic (subjective and quantitative) reactions are included in [Section 9.2.2](#).

Grading scales for clinical safety laboratory AEs are included in [Section 9.2.3](#).

If any of the halting rules are met following any subject receipt of any study vaccination, then this trial will not continue with the remaining enrollments or study vaccinations without a review by and recommendation from the DSMB to proceed.

DMID retains the authority to suspend additional enrollment and study interventions/administration of study product during the entire trial, as applicable.

The DMID Medical Monitor is empowered to stop enrollment and study vaccinations if AEs that meet the halting criteria are reported.

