11.6.1 Analysis Populations

The Safety Analysis population includes all subjects who received at least one dose of study vaccine.

The modified intent-to-treat (mITT) population includes all subjects who received at least one dose of study vaccine and contributed both pre- and at least one post-study vaccination venous blood samples for immunogenicity testing (HAI or Neut antibody assays) for which valid results

were reported. For analyses using the mITT population, subjects in Group 2 who discontinue treatment after receiving the single IIV4 dose (Dose 1) but prior to receiving the first dose of the H7N9 vaccine (Dose 2) will be analyzed with group 3. All other subjects will be grouped based on randomized treatment arm.

The per protocol (PP) population includes all subjects in the mITT subset with the following exclusions:

- Data from all available visits for subjects found to be ineligible at baseline.
- Data from all visits subsequent to major protocol deviations, such as:
 - Second or third study vaccination not received,
 - Second or third study vaccination received out of window,
 - Receipt of non-study licensed live vaccine within 30 days before or after each study vaccination,
 - Receipt of non-study licensed inactivated vaccine within 14 days before or after each study vaccination,
 - Receipt of immunosuppressive therapy (e.g., corticosteroids) within 30 days before or after each study vaccination.
- Data from any visit that occurs substantially out of window.

For analyses using the PP population, subjects will be grouped based on study vaccinations received.

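### The four 7% halting rules count only reactions after H7N9 vaccine, but as worded their base can include Group 2 subjects who have so far had only IIV4

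*Protocol*

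**What the plan says.** Section 9.5 of the protocol opens by restricting what can count: "For the purpose of halting rules only events that occur following the administration of the" AS03-adjuvanted 2017 H7N9 vaccine will be considered. Four percentage rules follow, for Grade 3 injection site, subjective systemic, quantitative systemic and laboratory events. Each is met when at least 7% of subjects, and at least three, have the same vaccine-related reaction. The base in each is the Group 1 and 2 subjects "who received at least one dose of study vaccine to date, cumulative to all 2017 H7N9 vaccine administrations" (the last three bullets have the singular).

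Other parts of the protocol use the same vocabulary for IIV4:

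- Table 1 labels the Day 1 treatment of Group 2 "Dose 1 (First Study Vaccination): IIV4".
- Section 8.1.3 calls the Day 1 injection a dose of study vaccine, and in Groups 2 and 3 that injection is IIV4.
- Section 11.6.1 says "The Safety Analysis population includes all subjects who received at least one dose of study vaccine", and its mITT rule, built on the same phrase, expressly provides for Group 2 subjects who stop after IIV4 and before any H7N9 dose.

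Within 9.5 the SAE rule is worded precisely: "Any subject experiences an SAE from the time of the first 2017 H7N9 vaccination through 14 days after each 2017 H7N9 vaccination". SAP section 6.6.1 says only that the rules in protocol 9.5 will be monitored.

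**The concern.** A percentage stopping rule needs a numerator and a base drawn from the same people. Here the numerator is limited to subjects who have had H7N9 vaccine, while the literal base also holds Group 2 subjects waiting for their first H7N9 dose, or who never receive it. They dilute the percentage without being able to add to the count. The clause about H7N9 administrations may have been meant to narrow the base, but it can equally be read as describing which events accumulate.

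Two people applying the rule on the same day could therefore reach different answers. Because the trigger cannot fall as the base grows, the literal reading can only delay a halt. The delay matters because the vaccine "has not previously been evaluated in humans" (protocol 2.3.1), so more people would be exposed before the DSMB looks at a repeated Grade 3 reaction. Group 3 and the six halting rules without a percentage are not affected.

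**Working it through.** The documents give no trigger count or operating characteristic for the 7% rule, so there is no stated figure to reproduce.

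**Inputs.** From the documents: 60 subjects in each of Groups 1 and 2; 7% with a floor of 3 (9.5); first H7N9 dose in Group 2 at 21 to 28 days after IIV4 (8.3.3, SAP 4.4.5); about 12 weeks of enrolment (section 5). Assumed: even accrual, so 120/12 = 10 Group 1 and 2 subjects per week; no dropout; the rule checked at every event.

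**Trigger count.** Trigger = max(3, 0.07 × base rounded up).

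- Base 42: 2.94, so 3. Base 43: 3.01, so 4.
- 57 exposed: 3.99, so 4. The 72 dosed at that time: 5.04, so 6.
- 105 exposed: 7.35, so 8. The 120 dosed: 8.4, so 9.
- 114 exposed: 7.98, so 8. 115 exposed: 8.05, so 9.

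The readings agree up to 42 dosed, where the floor governs, and again once 115 have had H7N9. In between, with exposed = 5 × week + 5 × (week − lag in weeks):

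| Time, lag | Dosed | Exposed | Literal trigger (as % of exposed) | Exposed-only trigger (as % of exposed) |
|---|---|---|---|---|
| Week 6, 21 days | 60 | 45 | 5 (11.1%) | 4 (8.9%) |
| Week 9, 21 days | 90 | 75 | 7 (9.3%) | 6 (8.0%) |
| Week 12, 21 days | 120 | 105 | 9 (8.6%) | 8 (7.6%) |
| Week 6, 28 days | 60 | 40 | 5 (12.5%) | 3 (7.5%) |
| Week 12, 28 days | 120 | 100 | 9 (9.0%) | 7 (7.0%) |

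Day by day, a gap exists on about 67 days at a 21-day lag and is 2 on about 2 of them; at a 28-day lag the figures are 74 and 21 days.

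**Chance of halting, and exposure at halt.** Simulation with 20,000 runs per setting, 21-day lag, random order of 60:60, one given Grade 3 reaction occurring 2 days after a dose, each subject counted once. Three event models:

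- (a) events after the first H7N9 dose only, with probability p;
- (b) the same p independently at both doses, the second given only to subjects without a first-dose event, since section 5.2.3 withholds it after a Grade 3 event without alternative aetiology;
- (c) as (b), but with rate c per subject over both doses, so the per-dose rate is 1 − √(1 − c).

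Entries are literal v exposed-only. Exposure is the mean number with at least one H7N9 dose at halt, in runs where both readings trigger.

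| Model | True rate | Ever halts | Exposed at halt |
|---|---|---|---|
| (a) | 3% | 6.6% v 15.1% | |
| (a) | 5% | 29.1% v 45.7% | |
| (a) | 8% | 74.0% v 84.5% | 46.3 v 36.1 |
| (a) | 10% | 90.7% v 95.2% | 40.1 v 32.2 |
| (b) | 8% | 99.8% v 99.8% | 40.7 v 33.8 |
| (b) | 10% | 100% v 100% | 31.3 v 27.6 |
| (c) | 3% | 2.8% v 7.3% | |
| (c) | 5% | 19.8% v 30.5% | |
| (c) | 8% | 66.9% v 75.4% | 73.2 v 56.6 |
| (c) | 10% | 87.5% v 91.1% | 64.8 v 50.4 |

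At a 28-day lag and 10% (10,000 runs), model (a) gives 89.9% v 95.5% with 44.8 v 31.7 exposed, and model (b) 100% v 100% with 32.3 v 26.4 exposed.

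**Dropout.** If 9 Group 2 subjects (15% of 60, assumed) never received H7N9, the difference would persist to the end: 0.07 × 120 = 8.4, so 9, against 0.07 × 111 = 7.77, so 8.

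**The case against.** The strongest reply is that 9.5 already shows what was meant. Its first sentence is limited to H7N9, the percentage rules to the H7N9 arms, and the clause on H7N9 administrations adds nothing to the base unless it narrows it. Usage elsewhere is mixed: sections 3.1.3 and 6.2 sometimes use the study-vaccine term for the H7N9 product, and 2.1.1 and 14.7 name H7N9 vaccine and AS03 as the study products. The DSMB charter, which is not available here, may settle the matter. This makes the exposed-only reading the likely intention. It does not make it the text, and a threshold should not depend on inference.

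The effect is also small, and mean exposure overstates the typical case. In a re-run of 4,000 simulations at a 21-day lag, the median number of extra subjects exposed was 1 at 8% and 0 at 10% in models (a) and (b), and 7 and 5 in model (c). In model (a) the readings halted at the same point in 47% and 53% of runs. That stands.

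Finally, the fix has a price. In model (a) at a true 5% it raises halting by 45.7 − 29.1 = 16.6 points, more than the 84.5 − 74.0 = 10.5 points gained at 8%. A halt suspends vaccination, and the later-dose windows of +7 days allow no exceptions. This also stands. But a halt means DSMB review, not termination, and those extra halts are what a 7% rule gives when applied to the people at risk.

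Other protections remain: the six other halting rules, the individual rule withholding further doses after a Grade 3 event, the DSMB reviews at 25% and about 75% of participants, and the stopping authority of DMID and the Medical Monitor.

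**Conclusion.** The concern holds. As written, the base of the four 7% rules is ambiguous, and its literal reading includes subjects who cannot yet contribute an event. That the ambiguity exists is clear from the text. The consequence is conditional on the literal reading being applied, which the available documents neither confirm nor exclude.

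The consequence is minor to moderate: a trigger 0 to 2 subjects higher during accrual, usually 1 at the 21-day lag. The loss in the chance of halting at a true 8% ranges from none (model b) to about 10 points (model a), with on average 7 to 17 more subjects exposed at halt across the three models. These figures rest on even 12-week accrual and assumed Grade 3 rates, since the documents give none. Faster accrual or a longer lag would widen the gap. The wording should be corrected because it is a safety decision rule and the error can run only in the less protective direction.

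**What to change.** In the four 7% bullets of protocol 9.5, change the base from recipients of at least one dose of *study vaccine* to recipients of at least one dose of *AS03-adjuvanted 2017 H7N9 IIV*, keeping the restriction to Groups 1 and 2. Optionally, make the same change from *any study vaccination* to *any 2017 H7N9 vaccination* in the 7-day lead-in and in the closing sentence on meeting a halting rule; the first sentence of 9.5 already restricts the events.

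The cost is an edit to protocol wording, with no added subjects, visits or procedures. If the literal reading would otherwise have been used, expect more halts for DSMB review when the true rate is below 7%: 46% against 29% at 5%, and 15% against 7% at 3%, in the first-dose model.

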9.6 Safety Oversight

9.6.1 Independent Safety Monitor (ISM)

The ISM is a physician with relevant expertise whose primary responsibility is to provide independent safety monitoring in a timely fashion. **For this trial, an ISM is not required.** However, at each participating VTEU site, and at the request of DMID, in real time, the principal investigator should be able to identify an independent physician to function as an ad hoc ISM. That person should have the privileges to examine the subject, review the subject's medical and study records, and provide an independent medical assessment and recommendation to DMID.

9.6.2 Data and Safety Monitoring Board (DSMB)

Safety oversight will be conducted by a DSMB that is an independent group of experts that monitors subject safety and advises DMID. The DSMB members will be separate and independent of study personnel participating in this trial and should not have scientific, financial or other conflict of interest related to this trial. The DSMB will consist of members with appropriate expertise to contribute to the interpretation of the data from this trial. The DSMB will operate under the rules of a DMID-approved charter that will be written at the organizational meeting of the DSMB. Procedures for DSMB reviews/meetings will be defined in the charter. Reports may include enrollment and demographic information, medical history, concomitant medications, physical assessments, clinical laboratory values, dosing compliance, solicited and unsolicited AE/SAEs, and HAI and Neut antibody assay results. The DSMB will review SAEs on a regular basis and ad hoc during this trial. The DMID Medical Monitor and the ISM (as deemed necessary) will be responsible for reviewing SAEs in real time.

The DSMB will review study progress and participant, clinical, safety, and reactogenicity data at the following time points:

- Data review for safety at study specific time frames; at least annually.
- Electronic review when 8-day reactogenicity and clinical safety laboratory data following the first study vaccination is available for 25% of study participants.
- Approximately when 8-day reactogenicity and clinical safety laboratory data following the first study vaccination is available for 75% of study participants.
- Final review meeting: 6 to 8 months after clinical database lock to review the cumulative unblinded safety and immunogenicity data for this trial. The data will be provided in a standard summary format. The DSMB may be asked to provide recommendations in response to questions posed by DMID.
- Ad hoc when a halting rule is met, for immediate concerns regarding observations during this trial, or as needed.

Additional data may be requested by the DSMB, and interim statistical reports may be generated as deemed necessary and appropriate by DMID. The DSMB may receive data in aggregate and presented by treatment arm, including expected and observed rates of the expected AEs. The DSMB will review grouped data in the closed session only. As an outcome of each review/meeting, the DSMB will make a recommendation as to the advisability of proceeding with study vaccinations (as applicable), and to continue, modify, or terminate this trial.

The DSMB will operate under the rules of a DMID-approved charter that will be written at the organizational meeting of the DSMB. At this time, each data element that the DSMB needs to assess will be clearly defined. Procedures for DSMB reviews/meetings will be defined in the charter. The DSMB will review applicable data to include, but not limited to, study progress and participant, clinical, safety and reactogenicity data. Reports may include enrollment and demographic information, medical history, concomitant medications, physical assessments, clinical laboratory values, dosing compliance, solicited and unsolicited AE/SAEs, and HAI and Neut antibody assay results.

DMID or the DSMB chair may convene the DSMB on an ad hoc basis according to protocol criteria or if there are immediate concerns regarding observations during the course of this trial. The DMID Medical Monitor is empowered to stop enrollment and study vaccinations if AEs that meet the halting criteria are reported. The DMID Medical Monitor and the ISM (as deemed necessary) will be responsible for reviewing SAEs in real time. The DSMB will review SAEs on a regular basis and ad hoc during this trial.

10 CLINICAL MONITORING

10.1 Site Monitoring Plan

Site monitoring is conducted to ensure that the human subjects' protections, study and laboratory procedures, study intervention administration, and data collection processes are of high quality and meet sponsor, ICH/GCP guidelines and applicable regulations, and that this trial is conducted in accordance with the protocol, protocol-specific MOP and applicable sponsor SOPs. DMID, the sponsoring agency, or its designee will conduct site-monitoring visits as detailed in the clinical monitoring plan.

Site visits will be made at standard intervals as defined by DMID and may be made more frequently as directed by DMID. Monitoring visits will include, but are not limited to, review of regulatory files, accountability records, eCRFs, ICFs, medical and laboratory reports, and protocol and GCP compliance. Site monitors will have access to each participating VTEU site, study personnel, and all study documentation according to the DMID-approved site monitoring plan. Study monitors will meet with site principal investigators to discuss any problems and actions to be taken and document visit findings and discussions.

11 STATISTICAL CONSIDERATIONS

11.1 Introduction

The goal of this clinical trial is to assess, in healthy adults ages 19 – 64, the safety, reactogenicity, and immunogenicity of a pre-pandemic AS03-adjuvanted 2017 H7N9 IIV when two doses are administered 21 days apart either sequentially or simultaneously (within 15 minutes) with licensed seasonal influenza vaccine. Primary immunogenicity objectives include evaluating interference with response to 2017 H7N9 IIV vaccine virus strain 21 days post dose 2, and evaluating interference with response to seasonal influenza virus strains 21 days post receipt of IIV4.

